Tertiary outcomes will include measures of the patient-provider relationship- relationship commitment, patient-provider trust, patient anxiety in the interaction, patient trust in healthcare, discrimination in medical setting, Health literacy, health intake, and patient trust in medical technology at the pre-intervention (baseline) and post-intervention (12 month) periods.

Relationship commitment: In this study, we operationalize relationship commitment as patients' commitment to maintain care with their PCP when ALTA is introduced into their site. To assess patients' *perceived commitment* to their PCP, we will utilize the self-report measure developed by Berry et al. in a sample of primary care patients. The 5-item measure asks patients to rate their degree of commitment to the relationship with their doctor on a 7-point Likert scale (*strongly disagree* to *strongly agree*). Sample items include: *The relationship with my doctor is...something I am committed to; something I care about; and important to me.* To assess the *behavioral and affective indicators* of relationship commitment we will use natural language processing (NLP) and analyze text of patient-provider interactions that occur in the 12 months prior to ALTA, and over the 12 months ALTA phase. Data will be extracted from the EHR (e.g., clinical notes, messages, and free text) and MyChart to conduct these analyses.

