Medication adherence will be assessed via pharmacy refills obtained from prescription orders in the clinic EHR using the proportion of days covered (PDC) metric. The PDC is calculated as the total number of days covered by the medication divided by the number of days between the first fill of the medication in the study period and the end of the study period. Thus, as opposed to other pharmacy refill metrics, the PDC accounts for non-persistence with medications by tracking medications during the study period despite early discontinuation. We will count the days the patient was covered by each of their prescribed antihypertensive medications based on the prescription fill date and days of supply. If prescription fills for the same medication overlap, then we will adjust the prescription start date to be the day after the previous fill has ended. Patients will be considered adherent if they fill $\geq 80\%$ of their antihypertensive medications over the 12 months.

Tertiary Outcomes

Relationship commitment: To assess patients' *perceived commitment* to their PCP, we will utilize the self-report measure developed by Berry et al. in a sample of primary care patients. The 5-item measure asks patients to rate their degree of commitment to the relationship with their doctor on a 7-point Likert scale (*strongly disagree* to *strongly agree*). Sample items include: *The relationship with my doctor is...something I am committed to; something I care about; and important to me.* This measure will be administered to patients at baseline and 12 months.

To assess the *behavioral and affective indicators* of relationship commitment we will use NLP and analyze text of patient-provider interactions that

Part of the clinical interaction	Examples of relationship commitment behaviors and affect	Measurement strategy
Initiating the session	Patient and PCP creates a warm and friendly environment; collaboratively identify reason for visit and negotiate agenda	Sentiment analysis to identify affective behaviors (warmth, cheerfulness, and attentiveness) ¹⁰⁸

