Gathering information	PCP use of questions to explore a patient's problem and creates opportunities for patients to express concerns and ask questions; looks for potential barriers to communication (e.g., language, anxiety). Patient provides a complete medical history and information on current behaviors and condition from their perspective	Lexicon dictionaries (e.g., Linguistic Inquiry and Word Count (LIWC)) to identify interrogatives - e.g., asking questions ¹⁰⁵
Explanation and planning (shared decision-making)	PCP gives succinct, jargon-free information and checks patient understanding; actively involves patient in decision making process, and respects patient's decision Patient communicates their level of understanding and ask PCP to clarify information; adds perspective on treatment plans and agrees on what is feasible	LIWC to identify presence of assent words, absence of interaction qualities that inhibit openness, i.e. negative affect, anxiety, use of tentative words. ¹⁰⁵
Closing the session	PCP provides a summary of the discussion, verifies plan, and clarifies future expectations. Patient agrees on plan; clarifies what s/he should do between visits	To identify lexicons associated with closing rituals of speech acts with LIWC, and DAMSL. ^{108,107}

occur in the 12 months prior to ALTA, and over the 12 months ALTA phase. Data will be extracted from the EHR (e.g., clinical notes and free text) and MyChart secure messages to conduct these analyses. Table 1 provides examples of how we will examine patients' and providers' commitment to one another, and the associated measurement strategy, as they occur across different parts of the clinical interaction.

Patient-provider trust: To assess perceived patient-provider trust we will administer patient and provider measures developed by Thom et al. at the baseline and 12-month visit.

Patient: The 11-item Trust in Physician Scale (TPS) assesses a patient's interpersonal trust in their doctor. Responses are given on a 5-point Likert scale ranging from *totally disagree* to *totally agree*. Sample items include: “*I doubt that my doctor really cares about me as a person*” and “*If my doctor tells me to do something, then it must be true.*” The TPS has high internal validity ($\alpha=0.89$) and adequate test-retest reliability in a primary care sample. Prior research has found that TPS scores are associated with continuity of care, medication adherence, and satisfaction with care.

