be rigorously trained on both the coding scheme and on the use of Atlas.ti. Initial coding by the coders will be reviewed by either [name] or [name] and any corrections to the coding will be made and/or additional coder training. Following this period, two coders will independently code at least 10 interviews. At this point we will establish the inter-rater reliability and if it is inadequate (Krippendorff's $\alpha < 0.80$) the Data Management and Analysis Subcommittee will work collaboratively to refine and/or clarify the coding scheme and provide additional coder training. Double coding will continue until adequate inter-rater reliability is achieved. Coding the data will allow us to fully describe the themes and the prevalence of specific themes and sub-themes. Following the procedures in our previous trials (e.g., ALMA trial), we will audiotape and archive MA-led health coaching sessions, of which 10% will be coded using the Health Coaching Evaluation Checklist. The checklist assesses the degree to which the MAs are correctly using their coaching techniques and are achieving the desired impact with patients. We will apply the same coding methods as the narrative reports and interviews. Briefly, two members of the study team will be rigorously trained by the Data Management and Analysis Subcommittee to apply the checklist to the tapes, and supervised by [name]. The coders will listen to the audiotapes twice, the first review will be done to get a sense of the session flow and MA counseling style; the second to code the interaction. We will establish inter-rater reliability after the two coders independently code at least 10 tapes, and double coding will continue until adequate inter-rater reliability is achieved (Krippendorff's $\alpha > 0.80$).

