Maximum likelihood estimation of mixed-effects models will be used to account for missing data; this is equivalent to an assumption of data missing at random. We will conduct sensitivity analyses assessing this assumption. We will also compare participants with and without missing values in baseline and site characteristics, as well as intervention vs control group status; if differential patterns emerge, we will consider using multiple imputation and/or inverse probability weighting to adjust for missing data. For our behavioral measures of commitment and trust derived from text analysis, we will use Python with a dedicated suite of libraries for sentiment analysis and emotion detection. The text processing libraries will be used to complete the pre-processing steps including tokenization, stemming, and lemmatization. Tokenization is the process of separating text into smaller units, i.e., words, characters, or subwords. Stemming and lemmatization will be done to reduce inflectional forms and derive the common base form [e.g., am, are, is → be]. Next, each document (clinical notes, transcripts, secure messages) will be represented as vectors using word embeddings. Distributional semantics models (e.g., continuous Bag-of-Words, Skip-gram, Global vectors) will be used to represent each word as a vector while preserving the contextual information of the word before the training phase. Resources such as lexicons (e.g., LIWC, EmoLex) will be used for feature extraction representing presence or absence of emotion words, and words associated with opening or closing rituals of a conversation. Next, multiple supervised and unsupervised algorithms (e.g., attention-based neural models, transformers architecture) will be trained on the dataset and an optimized model will be established via several rounds of experiments and rigorous evaluations. Once the best fitting model is established, it will be used to train on clinical notes data before and after ALTA implementation. Patient and providers' sentiment will be compared to establish how the relationship has changed through ALTA participation. we will use GLMM to analyze the effect of ALTA on the tertiary outcomes of patient state anxiety, SBP, DBP, and PDC. Since each individual outcome is of interest, testing will be 2-sided with a Type I error rate of 0.05 and no adjustment for multiple testing.

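### The text-derived indicators of commitment and trust do not match their stated sources, and the before-after text comparison can register a change in charting as a change in the relationship

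*Combined protocol and SAP*

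**What the plan says.** Commitment and trust are each measured in two ways: by survey scales at baseline and 12 months, and by text analysis. This point concerns the text analysis only.

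**Sources.** Section 5.2.2 says "Data will be extracted from the EHR (e.g., clinical notes, messages, and free text) and MyChart to conduct these analyses". Section 6.1.4 repeats this almost unchanged: "Data will be extracted from the EHR (e.g., clinical notes and free text) and MyChart secure messages to conduct these analyses". For trust, both sections name clinical notes and MyChart messages. The windows are the 12 months before ALTA and the 12 months of ALTA.

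**Indicators.** The commitment table in 6.1.4 follows a visit from opening to close. The opening row reads "Patient and PCP creates a warm and friendly environment; collaboratively identify reason for visit and negotiate agenda"; the measurement entry for the closing row reads "To identify lexicons associated with closing rituals of speech acts with LIWC, and DAMSL". The rows between cover gathering information and shared decision-making.

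**Recordings.** Section 6.4.3.1 says "we will audiotape and archive MA-led health coaching sessions, of which 10% will be coded". Sections 6.3.2 and 6.3.6 describe audio recording of staff interviews. The consent wording in 3.3.2 covers surveys, interviews and audiotaped coaching visits.

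**Analysis.** Section 6.4.3.3 lists clinical notes, transcripts and secure messages as documents to be vectorised, and extracts features that include "words associated with opening or closing rituals of a conversation". After model selection it says: "Once the best fitting model is established, it will be used to train on clinical notes data before and after ALTA implementation". The next sentence compares the sentiment of patients and providers to establish how the relationship changed.

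**The concern.** A text score is useful only if the text can contain the behaviour being scored and if the same ruler is used before and after. Both are in doubt here. Several indicators are features of conversation, while the named sources are written records. In the before-after step, patient sentiment appears to be read from notes, which staff write. The intervention changes what staff write. The wording on training also leaves open whether both periods are scored by one model.

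At stake is a reported change in commitment or trust that is really a change in documentation, or partly a change in the scoring model. Section 4.4 goes on to relate changes in the relationship to changes in adherence and BP control, so a documentation artefact could carry into that analysis. Section 6.4.3.3 tests at 0.05 with no adjustment for multiple testing.

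**Working it through.** The plan states no figure on this point, so the check sets the sections side by side.

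**1. Indicators against sources.** The last two columns are my judgement.

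| Row of the 6.1.4 table | Feature scored | In MyChart messages? | In clinical notes? |
|---|---|---|---|
| Initiating the session | Warmth, cheerfulness, attentiveness | Affect yes; the opening of a visit no | Tone of the note's author only |
| Gathering information | Interrogatives | Yes | Rarely as either party's own question |
| Shared decision-making | Assent, tentative words, negative affect | The words yes; the visit exchange no | Reported by the author, at best |
| Closing the session | Closing speech acts | The close of a message thread, not of a visit | No |

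The trust example in 6.1.4, patient self-disclosure and the provider's response, can occur in messages.

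**2. Where could transcripts come from?** Transcribed patient-provider visits appear once, in 5.2.2, in a struck-through paragraph about patient anxiety. The transcripts or recordings described elsewhere are of coaching sessions and interviews. Neither supplies dialogue for the before window: coaching does not exist before ALTA, and exit interviews take place at 12 months. By section 5.1.1 the in-trial time before ALTA is 3 + 6 = 9 months, so 12 - 9 = 3 months of the before window precede the trial period and can come only from existing records. Figure 1 gives later cohorts longer usual care, but that does not create visit recordings.

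**3. What is compared?** Messages are among the documents vectorised, but the before-after sentence names clinical notes alone. The sentence after it reports on patients as well as providers. Taken literally, patient sentiment is inferred from staff-authored text.

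**4. Does the intervention change that text?** Yes. Table 1 in section 3.2 makes structured documentation of coaching, treatment plans, goals and action plans a component of ALTA, and 6.1.4 counts progress notes shared with the care team as dose. Hence

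change in note score = change due to the relationship + change due to documentation.

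Randomising when each site starts does not separate the two terms, because both begin with ALTA at each site.

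**5. Is there one ruler?** Write f for the scoring model.
- One model for both periods: mean f(after) - mean f(before) is on a common scale. This also holds if f is fitted to the pooled text.
- Separate models: mean f_a(after) - mean f_b(before) mixes a change in text with a change in model.

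The plan does not say which applies. It promises rounds of evaluation but gives no reference labels, held-out text or performance threshold.

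**6. Coverage of patient-written text.** MyChart use among the 700 survey patients is not given. If 30% to 70% sent any message (an assumption), then 0.30 x 700 = 210 to 0.70 x 700 = 490 have patient-written text. The number with text in both windows cannot be larger. This sizes coverage, not bias.

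**The case against.** The strongest reply has five parts.

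- MyChart messages are a named source in both parties' own words. Questions, assent, affect and self-disclosure can be scored there. This stands, and it matters most for trust.
- Section 6.1.4 presents the table as examples, and the EHR sources are introduced as examples too. This also stands: the lists are not closed. It does not supply a source of visit dialogue for the before period.
- The plan refers to a single best-fitting model, and training on the notes may be loose wording for applying the model to them. That is possible, and one pooled fit would keep a common scale. A reader might infer that the model is refitted in each period, so that the scores cannot be compared. The documents do not say this; they only fail to exclude it.
- Section 6.4.3.3 plans to triangulate the text results with exit interviews. This is a real check on meaning, but interviews held only at 12 months cannot show that scores from the two windows are comparable.
- These are tertiary outcomes with survey measures alongside, and the power calculation in 6.4.2 rests on BP control. This stands and limits the weight of the point.

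**Conclusion.** The concern holds for the text-derived indicators. Several describe visit dialogue that the named sources do not contain. The reference to transcripts in 6.4.3.3 has no described origin and is not reconciled with the struck-through text in 5.2.2. The before-after step reads patient sentiment from notes whose content ALTA itself alters, and comparable scoring across periods is not guaranteed.

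A reader might go further and conclude that commitment and trust cannot be measured at all, or that PCP visits are certainly never recorded. Neither follows. The survey scales are intact, messages can carry part of the construct, and the absence of visit recordings is an inference from silence set against an unexplained mention of transcripts.

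The bias cannot be sized from the documents. The conclusion rests on two assumptions: that notes mainly carry their authors' words, and that ALTA documentation enters the EHR text being analysed. It should be settled before any text is scored, but it does not threaten the primary fidelity outcome, BP control or medication adherence.

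**What to change.** In sections 6.1.4 and 6.4.3.3, with 5.2.2 made to agree:

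1. Reconcile the source list. Delete transcripts as an input, or state what they are and show that they exist in both windows.
2. State for each indicator which source and which author it is scored from. Take patient-side indicators from patient-written MyChart text. Drop or redefine those that need visit dialogue, unless a source for it is given.
3. Report note-based scores only as tone of provider documentation, with ALTA template and coaching notes excluded or analysed separately.
4. Replace the sentence on training with: one locked model, developed without phase labels (for example, cross-fitted by practice), is applied unchanged to all before and after text.
5. Report the number of patients with text in both windows.

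**Cost.** This is mainly wording and order of analysis, plus the IRB modification that section 7.4 requires for a protocol change. Cross-fitting adds some computation. The substantive cost is coverage: patient-side text outcomes would describe portal users only. That is a selected group, and section 3.1 itself raises limited technology access and low digital literacy in the populations these clinics serve. The survey scales should therefore remain the main measures of commitment and trust. Setting ALTA notes aside reduces the charting problem but does not remove it, since other notes may also change once ALTA starts.

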6.1.5 Intervention Administration

Practice facilitator staffing and training: We will leverage the existing network of trained practice facilitators in our Department at NYULH to hire two facilitators. Our facilitators are health professionals with a minimum of a master's degrees (e.g. MPH) who have clinical and managerial experience and have been working in primary care settings as a facilitator over the past two years. Our facilitators were previously trained at the University of Buffalo Practice Facilitator Training program. This training program was designed and developed by national experts who drew upon the AHRQ Practice Facilitation Handbook. This is a 92-hour course with 13 weekly 1.5-hour live online classes plus a 40-hour fieldwork practicum (shadowing an experienced facilitator) and 26 hours of reflective learning. The training includes 21 modules that cover the full range of topics for trainees to achieve the four core competencies of practice facilitators: data use to drive improvement, interpersonal skills, Health IT optimization, and quality improvement and change management methods. In the first year of the project, we will add curriculum components to meet the specific goals of this study (e.g. education on the updated HTN guidelines) as well as training tailored to the specific intervention components, including system changes that we propose to implement, and data extraction from EHRs. They will also receive trainings on human subjects research and data safety. In subsequent years of the project, they will receive booster trainings on the curriculum components, as needed. The training combines didactic sessions with case-based learning using "standardized practice" exercises and will also be incorporated into the fieldwork experience.

Practice facilitator supervision: Drs. [name] and [name] will serve as facilitation managers where they will provide the day-to-day oversight of the facilitators. Drs. [name] and [name] will meet weekly with Facilitators at the start of the week to review the schedule, anticipated challenges, the need for additional expertise or assistance from IT or other project staff, and to review the previous weeks tracking reports (Table 5). These meetings are meant to assist facilitators to 1) develop and maintain facilitative relationships, 1) maintain effective boundaries to allow the practice to build capacity, 3) acquire the content knowledge needed for the particular PF intervention, 4) monitor their panel of practices' progress through the stages of the intervention model and implementation of change concepts, 5) troubleshoot problems, and 6) review the structured weekly activity reports and monthly narrative reports

6.1.6 Reaction Management

In the event that any of the participants (patients and clinical and nonclinical staff) experience anxiety as a result of participating in the pre-implementation and/or implementation phases of this trial, we will provide a list of mental health services that are offered at no or low-cost through the NYU Brooklyn network of participating practices. If immediate attention is warranted, the clinic social worker and/or psychologist will be contacted.

6.2.1 Efficacy

The efficacy of the intervention will be assessed via the secondary outcomes, improved BP control and antihypertensive medication adherence, at 12 months. BP control will be assessed using the mean of the last two measurements recorded in the EHR during each of

the pre-intervention and post-intervention study periods (baseline and 12 months). Medication adherence will be assessed via pharmacy refills obtained from prescription orders in the clinic EHR using the proportion of days covered (PDC) metric over the course of the 12-month study.

6.2.2 Safety/Pregnancy-related policy

Patients who are pregnant or planning to become pregnant in the next 12 months are excluded from participation in this trial.

6.2.2.1 Adverse Events Definition and Reporting

The Principal Investigator (PI) will be responsible for quality control including reviewing and reporting adverse events. The plan will comprise the following elements:

- Adverse events will be reported to the IRB.
- A detailed plan to address serious events that may arise during study visits, such as blood pressure values that indicate a hypertensive emergency, is in place. Critical blood pressure values are defined as: 180/100 mm Hg or higher. In the event that the RA encounters such readings at any point in the study visit process, the following protocol will be triggered: (1) Let the participant know that these values are very high and recommend follow-up with his/her primary care provider; (2) Alert the study PI and contact the Project Manager to inform that such a reading has occurred; (3) Document all cases on Adverse Event Form. The Project PI and key personnel will meet every 6 months to review adverse events reports, participant complaints, if any, and dropout rates. Data will be provided at those meetings by the investigators on key variables that may indicate harm, including changes in blood pressure and cardiovascular risk profile.
- Any unexpected adverse reactions that are associated with the research and that are fatal or life threatening will be reported to the IRB within 24 hours of discovery. Any unexpected adverse events associated with the study that are moderate to severe in nature, but not life threatening, will be reported to the IRB in 5 days.
- Summaries of adverse events reports will be made to NIMHD in the yearly progress or report or, at the end of year 5, in the final report, unless the nature of a particular event is such that it bears immediate reporting to NIMHD.
- If a serious adverse event occurs as a result of the study, consideration will be given to stopping the study early. In the event of early stopping of the study, the IRB will be promptly notified.

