3.3.2 Potential Risks

Though we expect the level of risk due to this project to be minimal, potential risks may include the following:

Elevated blood pressure: Since this study focuses on reducing BP, all of the patients are required to have uncontrolled HTN to be eligible to participate. All patients will have a primary care provider as part of this study; however, it is quite conceivable that a patient may have elevated BP readings during the study that will require more aggressive management. The clinical care of any given patient will be entirely handled by the patient's primary care provider, and study participants will be made aware of this at the consent visit. Similarly, any medical problem that arises during study visits will be referred to the patient's provider. If at any study visit, BP is elevated >180 SBP or >110 DBP, the participant will be directed to seek medical attention immediately at the clinic. All such participants will be required to bring to the next study visit a signed document attesting that they sought care. The Program Manager will follow-up with the participant's primary care provider to ensure proper medical follow-up. These data will be reviewed periodically by the DSMB and will be reported to the NYU IRB until the end of Year 5.

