5.2.2 Secondary and Tertiary Outcome Variables (if applicable)

Secondary outcomes will be measures of clinical effectiveness—BP control and adherence to antihypertensive medications at the pre-intervention (baseline) and post-intervention (12 month) periods.

BP control, the major secondary outcome, will be defined as SBP <140 and DBP <90 mmHg. BP control will be assessed using the mean of the last two measurements recorded in the EHR during each of the pre-intervention and post-intervention study periods (baseline and 12 months). BP readings will be extracted from patients' EHR by trained RAs. We will use the last two recorded measures to reduce variability associated with multiple BP measurements being taken by different clinic staff. We will also examine the proportion of patients with BP control <130/80 mmHg in exploratory analyses to provide preliminary data on BP control rates of hypertensive patients when considering the new guidelines. We will also explore mean change in systolic and diastolic BP based on the mean of the last two recorded BP readings in the EHR during the pre- and post-intervention periods.

Medication adherence will be assessed via pharmacy refills obtained from prescription orders in the clinic EHR using the proportion of days covered (PDC) metric. The PDC is calculated as the total number of days covered by the medication divided by the number of days between the first fill of the medication in the study period and the end of the study period. Thus, as opposed to other pharmacy refill metrics, the PDC accounts for non-persistence with medications by tracking medications during the study period despite early discontinuation. We will count the days the patient was covered by each of their prescribed antihypertensive medications based on the prescription fill date and days of supply. If prescription fills for the same medication overlap, then we will adjust the prescription start date to be the day after the previous fill has ended. Patients will be considered adherent if

they fill $\geq 80\%$ of their antihypertensive medications over the 12 months. In addition, we will assess the extent of medication non-adherence and the associated reasons based on the survey developed by [name].

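### Sections 3.3.2 and 6.2.2.1 print different critical-BP rules for the same study visits, and the one presented as the hypertensive-emergency plan omits immediate referral

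*Combined protocol and SAP*

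**What the plan says.** Section 3.3.2 (Potential Risks) gives this rule: "If at any study visit, BP is elevated >180 SBP or >110 DBP, the participant will be directed to seek medical attention immediately", the place being the clinic. Two further steps follow. The first is documentary: "All such participants will be required to bring to the next study visit a signed document attesting that they sought care". The second is for the Program Manager to contact the participant's "primary care provider to ensure proper medical follow-up".

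Section 6.2.2.1 (Adverse Events Definition and Reporting) says that a detailed plan for serious events at study visits, "such as blood pressure values that indicate a hypertensive emergency, is in place". It then sets its threshold, "Critical blood pressure values are defined as: 180/100 mm Hg or higher", and applies it to readings the research assistant (RA) meets at any stage of a study visit. Step 1 is "Let the participant know that these values are very high and recommend follow-up with his/her primary care provider". Step 2 alerts the PI and the Project Manager. Step 3 is the Adverse Event Form.

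Section 7.8 promises a step-by-step algorithm for such events but prints no threshold and no step. Neither 3.3.2 nor 6.2.2.1 refers to the other.

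On timing, section 5.1.1 gives two study visits, at consent/baseline and at 12 months. Section 6.3.1 repeats this, but its list of visit times for patients also includes 15-minute QI interviews at 3 and 6 months.

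**The concern.** Staff who need to know what to do about a very high reading can land on either of two rules. The diastolic cut-offs are 10 mmHg apart (110 and 100), the inequalities differ (strictly above, against at or above), and the instruction to the participant differs (go now, against a recommendation with no time frame). The more cautious instruction sits in the risk description. The section that calls itself the emergency plan has the weaker one.

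Two things are at stake. One is participant safety: an RA working only from 6.2.2.1 would not send someone at 190/115 for immediate care. The other is consistent recording: whether a reading reaches the PI and an Adverse Event Form depends on how an unstated and/or is resolved. The enrolled patients have uncontrolled hypertension by design, and 3.3.2 itself accepts that readings needing more aggressive management may occur.

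**Working it through.** The plan states no figure to reproduce here. The check is a comparison of the two rules.

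**Definitions**
- A (3.3.2): SBP >180 or DBP >110.
- B-or (6.2.2.1, either pressure suffices): SBP ≥180 or DBP ≥100.
- B-and (6.2.2.1, both needed): SBP ≥180 and DBP ≥100.

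**Example readings**

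| Reading | A: immediate attention | B-or: PI alert and form | B-and: PI alert and form |
|---|---|---|---|
| 170/105 | no | yes | no |
| 180/95 | no | yes | no |
| 190/90 | yes | yes | no |
| 170/115 | yes | yes | no |
| 190/115 | yes | yes | yes |

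**Read as or.** SBP >180 implies SBP ≥180, and DBP >110 implies DBP ≥100. So every reading that meets A also meets B-or, and none is missed. The readings that meet B-or alone are DBP 100 to 110 with SBP ≤180, and SBP exactly 180 with DBP ≤110. The two rules then nest as a lower and an upper tier.

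**Read as and.** The readings that meet A but not B-and are SBP >180 with DBP <100 (such as 190/90), and DBP >110 with SBP <180 (such as 170/115). They get immediate attention and PCP contact under 3.3.2, but no PI alert and no Adverse Event Form.

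**Which reading is likelier.** The plan defines control by requiring both pressures to be low: "BP control, the major secondary outcome, will be defined as SBP <140 and DBP <90 mmHg". Failing control therefore means that either pressure is high. This favours the or reading, but by inference only.

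**Where both rules apply.** At 190/115, 3.3.2 sends the participant for care at once, while 6.2.2.1 recommends PCP follow-up with no time frame. Doing both is possible, but no section says to.

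**Proof of care**
- Reading at baseline, two-visit schedule (5.1.1): 12 − 0 = 12 months to the next study visit.
- Reading at baseline, QI interviews counted as visits (6.3.1): 3 − 0 = 3 months.
- Reading at the 12-month visit: no next study visit on either count, so the requirement cannot be met.

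The Program Manager's contact with the PCP does not depend on a visit, so it partly covers these gaps. It has no deadline.

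**The case against.** The strongest reply is that nothing in 6.2.2.1 cancels 3.3.2. Anyone above 180 systolic or 110 diastolic at a study visit is already to be sent for immediate attention, and on the likelier reading the two rules form a workable pair of tiers. That stands. A reader might infer that the rules contradict each other, or that the protocol has no immediate referral. The documents support neither. What remains is that the section staff would open for an emergency lacks the step and does not point to it.

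Exposure is the second reply. Outcome BP comes from the EHR, no listed visit has the RA measure BP, and consent may be given by telephone or REDCap. A reading met during chart review may already have been handled in clinic, where recommending PCP follow-up is reasonable. This limits the practical weight. Even so, both sections are written for study-visit readings.

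A separate procedure might set the tiers, since 6.2.2.1 says a plan exists and 7.8 promises an algorithm. That cannot be checked here. Section 6.2.2.1 does print its own steps, and those should be complete.

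A reader might also infer that the end of DSMB activity leaves these readings unreviewed, or that the Adverse Event Form is now the only printed step that records them. The documents do not support this. Section 3.3.2 limits its own provision: "These data will be reviewed periodically by the DSMB and will be reported to the NYU IRB until the end of Year 5". Section 7.8 dates the end of Year 5 to December 31, 2023, so the two sections agree on a deliberate change. Section 7.8 also says that monitoring by the PI continues. Section 6.2.2.1 has the PI alert and a six-monthly review of adverse events by the PI and key personnel, and 7.7 lists a physician medical monitor who reviews adverse events.

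**Conclusion.** The point holds as a participant-safety and event-recording fault in the wording, and it should be fixed. For one setting, the two sections differ in diastolic cut-off, inequality and participant instruction, and the self-described emergency plan omits immediate referral.

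Read as or, no reading that needs immediate care escapes the recording rule. Read as and, readings such as 190/90 and 170/115 do. The proof-of-care step fails outright after the final visit. After baseline the wait is between about 3 and 12 months, depending on whether the QI interviews count as study visits, which the protocol leaves unclear.

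The documents do not say how often such readings occur, and the visit procedures suggest seldom. There is no effect on the efficacy analysis, power or type I error.

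**What to change.** Print one tiered rule in both 3.3.2 and 6.2.2.1, with thresholds confirmed by the responsible clinicians and the IRB. An example:

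- SBP ≥180 or DBP ≥100: alert the PI and Project Manager, arrange PCP follow-up, and complete the Adverse Event Form.
- SBP >180 or DBP >110: all of the above, and immediate medical attention.

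State the or explicitly. Carry the same thresholds into the algorithm promised in 7.8, or refer to them there. Replace signed proof at the next study visit with Program Manager confirmation from the PCP within a set number of days.

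The cost is a short amendment and a staff memo. Design, endpoints, sample size and analysis do not change.
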